9.6.7 Ancillary Statistical Analyses

9.6.7.1 Within-Group Analyses

The effects of on-trial end point variables other than treatment modality on the per-subject rate of change in CIMT, arterial stiffness and cognition will be separately assessed. The parameters to be tested will include laboratory data (plasma insulin, lipids/CRP, hemoglobin A1c, coagulation factors, rheology parameters, inflammatory variables and nattokinase levels), clinical variables (blood pressure, body mass, waist:hip ratio, etc.), and lifestyle variables (dietary intake, physical activity, smoking, etc.). Baseline and on-trial values of these data will be collected in order to address questions of clinical significance within each treatment group such as: 1) which baseline characteristics have differential effectiveness on the rate of change in CIMT; and, 2) what is the role of changes in these variables on the rate of change in CIMT. These analyses will utilize mixed effects models and generalizing estimating equations with CIMT (arterial stiffness, cognition) as the dependent variable. Analyses will be conducted in the combined sample with a covariate included to control for treatment group. Interaction terms with treatment group will be introduced to test whether relationships between independent variables and the trial end point are of equal magnitude between the 2 study groups. Experiment-wise error rates in these analyses will be controlled. All participants contributing at least one follow-up ultrasound (or cognitive test) will be included in these analyses.

9.6.7.2 Modifiers of Treatment Efficacy

The extent to which treatment effects are modified by other subject-specific factors will be examined. Potential treatment effect modifiers include baseline CIMT, smoking status (on-trial smokers versus non-smokers), BMI, age and gender. The statistical significance of differences in the treatment effect by subgroup will be tested by inclusion of an interaction term (treatment by subgroup) in the efficacy models detailed above. For descriptive comparisons, treatment effect sizes will be computed for each level of the possible modifier.

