3.3 Screening Visit (SV)

A SV appointment is contingent upon fulfilling all pre-screening eligibility criteria **[FORM 1]**. At SV, the following will be performed:

1. Assign study identification (ID) number (see Section 3.4 for procedure)
2. Explanation of study aims, protocol, benefits, risks
3. Participants sign Informed Consent and HIPPA **[FORM 2]**
4. Participants complete forms covering contact and demographic information:
 - Participant Information Form **[FORM 3]**
 - Personal Information Form **[FORM 4]**

5. Pre-screening Telephone Questionnaire **[FORM 1]** eligibility criteria reviewed with participant
6. Ensure that soy, soy protein and isoflavone food supplements have been stopped at least one month prior to SV (see Section 3.2)
7. Administer the Cardiovascular Disease History Questionnaire **[FORM 5]** and confirm that participants have no clinical manifestations of cardiovascular disease.
8. Administer the baseline Bleeding Assessment Questionnaire **[FORM 6a]** and confirm that participants have no bleeding diatheses or bleeding tendencies
9. Participants administered baseline Smoking, Passive Smoking, Alcohol, Other Substance Use Questionnaire **[FORM 7a]**
10. Administer the Reproductive History Questionnaire **[FORM 8]** and confirm that female participants have not menstruated for at least 6 months
11. Participants administered questionnaires covering health information:
 - Medical History Questionnaire **[FORM 9]**
 - Modified Rose Questionnaire **[FORM 10]**
 - Claudication Questionnaire **[FORM 11]**
 - Cardiovascular Disease Risk Factor Assessment Form **[FORM 12]**
12. Administer the Nonstudy Medications Record **[FORMS 13,14]** and confirm that participants are not taking lipid-lowering medication
13. Administer History of Vitamin and Nutritional Supplement Use Questionnaire **[FORM 15]** and confirm that participants are not taking soy, soy protein and isoflavone food supplements
14. Obtain participant's blood pressure and pulse rate **[FORM 16]** and confirm that systolic blood pressure is ≤ 160 mmHg and diastolic blood pressure is ≤ 110 mmHg
15. Obtain and record participant's weight and height **[FORM 16]**
16. Carotid artery ultrasound examination performed (first baseline - see Section 4.2 for randomization procedure)
17. Fasting blood samples drawn and analyzed for:
 - Chemistry
 - CBC
 - Platelet count
 - Prothrombin (PT)/activated partial thromboplastin time (aPTT)
 - Lipids
 - C-reactive protein
 - Hemoglobin A1c

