9.6.2 Baseline Comparability

All participants will be compared between treatment arms with respect to demographic (e.g., age, race, gender), cardiac and other medical history factors, cardiovascular risk factors (including blood pressure, smoking status), dietary factors, baseline CIMT, vascular stiffness, cognition, plasma insulin, lipids/CRP, hemoglobin A1c, coagulation factors, rheology parameters and inflammatory variables. Analytical methods will include two-sample t-tests (or a non-parametric analog) for continuous variables and chi-square procedures for categorical variables. The significance level for all analyses will be set at a two-sided $\alpha=0.05$.

If multiple baseline laboratory measures are completed (e.g., at SV and at v00), the baseline value will be computed as the average of the screening measure and the v00 visit determined prior to intervention. All treatment group comparisons on baseline variables will be performed for the entire randomized study sample, for the group of participants with repeat ultrasounds, and for the group of participants without repeat ultrasounds.

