9.6.3 Comparison of On-trial Changes in Laboratory and Lifestyle Variables

Treatment groups will be compared with respect to on-trial levels and on-trial changes in plasma insulin, lipids/CRP, hemoglobin A1c, coagulation factors, rheology parameters and inflammatory variables. Study groups will also be compared for on-trial levels and on-trial changes of other factors that might confound the analysis of primary end point differences. These will include analysis of dietary factors (e.g., total calories, and total calorie-adjusted calories from total, saturated, polyunsaturated, and monounsaturated fats, calories from protein, calories from carbohydrates, and dietary genistein, daidzein, and glycitein), physical activity, cardiovascular risk factors (including blood pressure, smoking status), and use of relevant nonstudy medications (including antihypertensive and lipid-lowering medications). For descriptive purposes, on-trial laboratory, dietary, clinical, and physical activity variables will be computed as the average of all on-trial determinations, weighted by the length of time between determinations. On-trial smoking will be compared as percentage of smokers versus percentage abstainers; average on-trial smoking levels (cigarettes per day) will also be computed for smokers as the average of all on-trial determinations as above. For all laboratory and clinical measures, a change variable will be computed at each on-trial measurement time as: on-trial value minus baseline value. Changes in laboratory and clinical variables from baseline will be compared within each treatment arm using generalized estimating equations to account for the repeated measurements over the study period; the model-specified correlation structure of the repeated measures will be determined by examination of the observed correlation structure. The test that the model intercept differs from 0 will comprise the overall test for significant change from baseline; incorporation of covariates for time periods of the study will test for differential change from baseline over the study period. Comparison of on-trial levels and changes in laboratory and clinical variables across treatment groups will also use generalized estimating equations, with an added covariate for randomized treatment group; interaction terms of treatment group-by-study time period will test whether treatment group differences vary over the study period. Compliance with the study product will be compared across treatment groups, also using generalized estimating equations as described. All analyses will be performed for the entire study sample and for the group of participants whose overall study product compliance is $>80\%$. The significance level for all analyses will be set at a two-sided $\alpha=0.05$.

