9.6.5.1 Primary Efficacy Analysis: Carotid Artery IMT Analyses

The primary end point will be the per-subject rate of change in the right distal CCA far wall IMT. The rate of change in the right distal CCA far wall CIMT will be computed for each participant by fitting a regression line of CIMT on years since baseline ultrasound. The estimated slope of the regression line will be used as that subject's CIMT rate of change. Analyses of trial end points will be performed on the intent-to-treat sample, which will be defined as all randomized participants who had a baseline and at least 1 follow-up CIMT measurement taken after randomization.

The statistical approach outlined above will be accomplished using mixed effects models for longitudinal data, with the randomization stratification variable (dichotomized baseline CIMT) used as a covariate. Each CIMT measure will be included as a dependent variable. The regression coefficient associated with the model covariate of time on-study will estimate the average group progression rate of CIMT (in mm/year). Random effects terms for the regression intercept and slope (change over time) will allow for individual participant deviations from their group average in baseline CIMT and CIMT rate of change, respectively. The statistical test for differences in the CIMT rate by treatment group will be accomplished by adding a treatment group by time on-study interaction term. The significance of the regression coefficient associated with this interaction term is the test that the CIMT rates differ by treatment group. We will also evaluate baseline plasma levels of insulin, lipids/CRP, hemoglobin A1c, coagulation factors, rheology parameters and inflammatory variables, dietary nutrients, smoking, blood pressure, physical activity and use of non-study medications as potential confounders. If any of these variables are found to be confounders of treatment-rate of CIMT relationship, they will be included as

covariates in the analysis.

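### Section 9.6.7.2 forms the smoking subgroup from on-trial smoking, a post-randomization variable; baseline smoking, already collected, should define it, and the change is free

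*Combined protocol and SAP*

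**What the plan says.** Section 9.6.7.2 names five potential modifiers of the treatment effect: CIMT, smoking, BMI, age and gender. CIMT is labelled as baseline. Smoking is entered as "smoking status (on-trial smokers versus non-smokers". BMI carries no time point. Each modifier is "tested by inclusion of an interaction term (treatment by subgroup) in the efficacy models detailed above", and an effect size is to be reported for each level.

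Three other sections bear on how smoking is measured and used:

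- Section 9.6.3 keeps on-trial values apart from baseline values and compares them between arms: "On-trial smoking will be compared as percentage of smokers versus percentage abstainers". Smoking status is among the "other factors that might confound the analysis of primary end point differences".
- Section 3.3 schedules a smoking form at the screening visit, before randomization: "Participants administered baseline Smoking, Passive Smoking, Alcohol, Other Substance Use Questionnaire" (Form 7a). Section 9.6.2 uses smoking status in the comparison of arms at baseline: "cardiovascular risk factors (including blood pressure, smoking status".
- Section 9.6.7.1 counts smoking among the lifestyle variables, says "Baseline and on-trial values of these data will be collected", and adds interaction terms with treatment group.

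Section 9.6.7.2 gives no reason for using on-trial rather than baseline smoking. It also has no rule for a participant whose status changes during the trial.

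**The concern.** Randomization makes the arms comparable within any stratum fixed before treatment starts. It gives no such guarantee within a stratum formed afterwards. If something that follows from treatment assignment changes who is recorded as a smoker on trial, the active and placebo participants within a smoking stratum are no longer alike by design. The treatment-by-smoking contrast can then move away from its true value even when treatment has no effect.

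Two practical problems do not depend on that mechanism. With no rule for people who stop or start smoking, the classification would be settled after the data exist. And a participant can qualify for the efficacy models with early ultrasound data yet have no on-trial smoking record. At stake is how one ancillary subgroup result can be read.

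**Working it through.** **Step 1. Is the variable post-randomization?** Yes. Section 9.6.3 computes change as the on-trial value less the baseline value, so on-trial means after baseline throughout the plan. In 9.6.7.2 the baseline label on CIMT and the on-trial label on smoking stand in the same list.

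**Step 2. Is a baseline value available?** Yes. Form 7a is scheduled at screening (Sections 1.8 and 3.3), and smoking status is already used in 9.6.2.

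**Step 3. Could the on-trial value be missing for analysed participants?** The analysis set in 9.6.5.1 is "all randomized participants who had a baseline and at least 1 follow-up CIMT measurement taken after randomization". Section 9.3.3 places six on-trial ultrasounds at v06, v12, v18, v24, v30 and v36. The smoking row of Section 1.8 shows one screening mark and three on-trial marks; column alignment is damaged in the text available, so the months cannot be read. If the three are annual (an assumption), the first falls at v12, and someone whose only follow-up ultrasound is v06 would be analysed without an on-trial smoking value.

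**Step 4. How large could the bias be?** The documents give no smoking prevalence, quit rate or power for this interaction, so there is no stated figure to reproduce. The following is an illustration in which every input is assumed.

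- 4,000,000 simulated participants per scenario, 1:1 allocation, no treatment effect and no true interaction.
- Baseline smoking b: 10% or 20%. A latent factor U, standard normal, drives both smoking and outcome.
- Log-odds of on-trial smoking = (1.0 if baseline smoker, −4.0 if not) + U + shift × treatment.
- Outcome = 0.5U + 0.3b + 0.8 × standard normal noise.
- False interaction = (active − placebo among smokers) − (active − placebo among non-smokers).

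| Baseline smokers | Shift | On-trial smokers, active / placebo | On-trial split | Baseline split |
|---|---|---|---|---|
| 10% | 0 | 9.5% / 9.5% | 0.002 | 0.004 |
| 10% | −0.5 | 7.6% / 9.5% | 0.022 | −0.003 |
| 10% | −1.0 | 6.0% / 9.5% | 0.052 | −0.003 |
| 20% | 0 | 16.2% / 16.2% | 0.001 | 0.001 |
| 20% | −0.5 | 13.4% / 16.2% | 0.023 | −0.002 |
| 20% | −1.0 | 10.9% / 16.2% | 0.051 | −0.006 |

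The baseline column and the zero-shift rows are zero by construction; their departures are simulation noise. The outcome SD is √(0.25 + 0.09 × 0.1 × 0.9 + 0.64) = 0.948 with 10% smokers and √(0.25 + 0.09 × 0.2 × 0.8 + 0.64) = 0.951 with 20%. In SD units the bias therefore runs from 0.022/0.948 = 0.023 to 0.052/0.948 = 0.055.

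**Step 5. How does that compare with sampling error?** Take all 240 analysed, equal arms, unit SD and a smoker share p (assumed):

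SE = √[4/(240p) + 4/(240(1 − p))]; difference detectable with 80% power at two-sided 0.05 = 2.802 × SE.

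| p | Smokers | SE (SD) | Detectable (SD) |
|---|---|---|---|
| 5% | 12 | √(0.3333 + 0.0175) = 0.592 | 1.66 |
| 10% | 24 | √(0.1667 + 0.0185) = 0.430 | 1.21 |
| 20% | 48 | √(0.0833 + 0.0208) = 0.323 | 0.90 |

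The bias is at most 0.055/0.430 = 13% of one standard error with 10% smokers, and 0.054/0.323 = 17% with 20% (0.051/0.951 = 0.054).

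**The case against.** The strongest reply has four parts.

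**Blinding.** The trial is double-blinded and placebo-controlled with the same visit schedule in both arms (Section 1.3), and no section suggests that nattokinase changes smoking. If treatment does not shift smoking, the illustration gives no bias, and 9.6.3 would look for a shift by comparing on-trial smoking between arms. This stands, and it is why the likely bias is small. It does not supply a reason to prefer the on-trial variable.

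**Baseline smoking is already covered.** Section 9.6.7.1 collects baseline and on-trial smoking and adds treatment interaction terms, so a treatment-by-baseline-smoking interaction is arguably planned there. This largely stands. A reader might infer that the plan ignores baseline smoking as a modifier; the text does not support that. What remains is that the section written for effect modification uses the on-trial version, leaving two smoking interactions and no statement of which one addresses effect modification.

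**The contrast with the other modifiers.** A reader might infer that smoking is the only listed factor not fixed at baseline. Only CIMT is labelled as baseline. BMI has no time point, and Section 7.12.3 has weight measured at every later visit, so BMI could also be taken on trial. This stands, and the fix should cover BMI.

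**Precision.** Even a bias of 0.10 SD, well above the illustrated range, would be 0.10/0.430 = 23% of one standard error with 10% smokers. In heads, 10% of 240 is about 12 smokers per arm, so a gap of 15 percentage points in quitting is 12 × 0.15 = 1.8 people. Sampling error dominates. This stands too; the case for the change is validity and pre-specification, not a large expected bias.

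**Conclusion.** The point holds in a limited form. Section 9.6.7.2 explicitly conditions a treatment comparison on a post-randomization variable when a pre-randomization version exists. Comparisons within smoking strata lose the protection of randomization, people who change status are unclassified, and some early leavers may have no value.

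Bias needs treatment or differential follow-up to affect on-trial smoking. Under the assumed inputs it is zero without such an effect and about 0.023 to 0.055 SD with one, against a standard error of 0.32 to 0.59 SD for smoker shares of 20% down to 5%. All of these rest on assumed prevalences and an assumed latent link; none comes from the documents.

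Two stronger readings should be resisted. One is that the interaction will show a spurious modifier or hide a real one: the documents give no mechanism, and the illustrated bias is a small fraction of sampling error. The other is that the efficacy conclusions are compromised: this is one ancillary analysis, and the primary CIMT, co-primary stiffness and secondary cognition comparisons do not use the subgroup. The right label is a free improvement.

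**What to change.** In Section 9.6.7.2, define the smoking modifier as smoking status at baseline, taken from the screening smoking questionnaire (Form 7a), and write BMI as baseline BMI. The documents give the title of Form 7a but not its items, so the exact categories should be set from the form and written into the SAP before unblinding.

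Leave on-trial smoking where it already serves a purpose: the comparison of arms in 9.6.3 and the analyses of lifestyle variables in 9.6.7.1. Removing it from 9.6.7.1 is not needed. One added sentence should say that results based on on-trial smoking are non-randomized associations.

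The cost is a wording change. It needs no new data, form, visit or participant.

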1.1 Executive Summary

The potential for nattokinase to “thin” blood and to reduce blood clotting by positive antithrombotic and fibrinolytic effects presents a unique opportunity to safely study such effects on cardiovascular disease (CVD) and cognition. Unfortunately, such studies of antithrombotic and fibrinolytic pathways of prevention have been limited due to lack of safe compounds and the adverse reactions associated with current agents such as Coumadin. Nattokinase, an over-the-counter supplement used for cardiovascular health, is the most active functional constituent of natto, a fermented soy product. Natto has been consumed primarily by the Japanese for over 1000 years, a population with one of the lowest risks for CVD and dementia. CVD and dementia remain the most challenging age-related health risks of the 21st century for Americans necessitating development of further effective preemptive strategies. Whether reducing the propensity for thrombus formation and/or increasing fibrinolytic activity can prevent the progression of atherosclerosis and cognitive decline has not yet been determined.

Using nattokinase under primary prevention conditions, we propose to conduct a randomized, double-blinded, placebo-controlled trial to determine whether decreasing atherothrombotic risk can reduce the progression of atherosclerosis and cognitive decline. We propose to randomize 240 healthy non-demented women and men to nattokinase supplementation or to placebo for three years. The primary trial end points will be measurement of carotid arterial wall thickness and arterial stiffness, early changes of atherosclerosis that can be measured safely by non-invasive imaging techniques. The secondary trial end point will be ascertained through change in cognition measured by a neuropsychological battery. In addition, biochemical blood measurements and in vitro studies will be conducted to compare the effects of nattokinase relative to placebo on blood coagulation and thrombus break-down capabilities, blood flow properties, inflammation and inflammatory activation of endothelial cells that line blood vessels.

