4.2 Randomization Procedure

Active nattokinase and matching nattokinase placebo will be shipped directly to the DCC by Jarrow Formulas. Active nattokinase and matching nattokinase placebo will be shipped on different days separated in time by at least one week. Jarrow Formulas will clearly label the containers as active nattokinase and nattokinase placebo. Active nattokinase and matching nattokinase placebo capsules will be sealed in white plastic bottles with a quantity of 110 capsules per bottle. Each participant will be given adequate numbers of bottles of capsules for the period of time between clinic visits. The bottles of capsules will be prepared by the DCC for each randomized participant and will be dispensed at each clinic visit to each participant. The bottles of capsules will contain an attached label prepared with the following identifiers: Stratum (1,2) and a unique identification number for each bottle of capsules. The label will also contain space for the participant's name, visit number and date of dispensation to be filled in by clinic personnel when the bottle of capsules is assigned to a randomized participant.

The DCC will generate randomization lists for 2 strata with a blocking factor not identified to other study personnel:

- 1) Right distal common carotid arterial far wall IMT ≥ 0.75 mm
- 2) Right distal common carotid arterial far wall IMT < 0.75 mm

As the Final Eligibility Check List **[Form 17]** is completed and a participant is found to be eligible for randomization, the clinic coordinator will do the following:

- 1) Using the appropriate stratum (identified in the Eligibility Summary section of the Final Eligibility Check List **[Form 17]**, refer to the study randomization log for that stratum.
- 2) The study randomization log contains a separate list of sequential study product ID numbers for each stratum. Note that each stratum list has a column of study product ID numbers as well as a blank column to list the participant study ID. On the study randomization log for the appropriate stratum, write the participant study ID on the next available line. Note the study product ID number.
- 3) Write the study product ID number in the **product ID number item** of the Eligibility Summary section on the Final Eligibility Check List **[Form 17]**.

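### Section 9.6.7.2 tests effect modification by baseline CIMT, BMI and age by subgroup, without stating groups or cut points; a continuous interaction would keep information that grouping loses under a roughly linear gradient.

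*Combined protocol and SAP*

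**What the plan says.** The list in section 9.6.7.2 mixes two kinds of variable: "Potential treatment effect modifiers include baseline CIMT, smoking status (on-trial smokers versus non-smokers), BMI, age and gender". Gender and smoking, as described there, are categorical. Baseline CIMT, BMI and age are continuous.

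One significance test is given for all five: "The statistical significance of differences in the treatment effect by subgroup will be tested by inclusion of an interaction term (treatment by subgroup"). A separate sentence, for description, adds that "treatment effect sizes will be computed for each level of the possible modifier". The section does not say how many levels BMI, age or baseline CIMT will have, where the cuts fall, or whether ordered groups would be scored as a trend.

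Groups for CIMT appear only in the randomization. Section 4.2 defines two strata, at or above 0.75 mm and "Right distal common carotid arterial far wall IMT < 0.75 mm". Section 9.6.5.1 carries this into the efficacy model, "with the randomization stratification variable (dichotomized baseline CIMT) used as a covariate". Neither section says that this cut also defines the subgroups of 9.6.7.2.

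The neighbouring section 9.6.7.1 plans treatment interactions for laboratory, clinical (including body mass) and lifestyle variables: "Interaction terms with treatment group will be introduced to test whether relationships between independent variables and the trial end point are of equal magnitude". It mentions no grouping. It does not name age or baseline CIMT.

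**The concern.** Groups are needed for a table of effects by subgroup. They are not needed for the significance test, which can use each participant's actual age, BMI or wall thickness. A grouped test treats everyone within a group as alike and so discards the within-group part of any gradient.

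Two things are at stake. A real gradient of benefit is more likely to be reported as no modification. And with no cut points stated, the answer depends on where the cuts are placed, a choice that could be made after the data are seen. The point applies to the CIMT, stiffness and cognition models alike.

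**Working it through.** The documents give no power, effect size or variance for any interaction, so there is no figure of the plan's to reproduce. The check asks how much a continuous interaction test loses when its modifier is grouped.

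**Inputs**
- Modifiers and form of test: section 9.6.7.2.
- Significance level: two-sided 0.05. Section 9.6.2 sets this for baseline comparisons ("The significance level for all analyses will be set at a two-sided" 0.05) and 9.6.3 for on-trial comparisons. It is not restated for effect modification, so it is assumed here.
- Sample size, used only in the simulation: section 1.1, "We propose to randomize 240 healthy non-demented women and men", taken as 120 per arm (1:1 assumed).
- Assumptions of this check: a normal modifier, a linear gradient, and full-scale power of 30%, 50% or 80%.

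**Information kept by a two-group split.** With share p in one group, z_p the normal quantile at p and φ the normal density, the share kept is E = φ(z_p)² / [p(1 − p)].
- 50/50: 0.3989² / 0.25 = 0.637 (that is, 2/π)
- 70/30: 0.3477² / 0.21 = 0.576
- 80/20: 0.2800² / 0.16 = 0.490

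**Power after the split.** Power = Φ[(1.960 + z_power) × √E − 1.960]. With E = 1 this returns the starting power.
- From 80%, median split: 2.802 × 0.798 − 1.960 = 0.275, so power is 60.8%.
- From 80%, 80/20 split: 2.802 × 0.700 − 1.960 ≈ 0, so power is 50.0%.
- From 50%, median split: 1.960 × 0.798 − 1.960 = −0.396, so power is 34.6%.
- From 50%, 80/20 split: 1.960 × 0.700 − 1.960 = −0.588, so power is 27.8%.

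| Split | Kept | From 80% (loss) | From 50% (loss) | From 30% (loss) |
|---|---|---|---|---|
| 50/50 | 63.7% | 60.8% (19.2) | 34.6% (15.4) | 20.9% (9.1) |
| 70/30 | 57.6% | 56.6% (23.4) | 31.8% (18.2) | 19.3% (10.7) |
| 80/20 | 49.0% | 50.0% (30.0) | 27.8% (22.2) | 17.1% (12.9) |

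The 30% column also counts the small opposite tail.

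**Simulation.** A regression with one outcome per participant, N = 240 and 4,000 replicates agrees. A median split takes power from 50% to 34% and from 79% to 59%. An 80/20 split takes it from 48% to 27% and from 79% to 48%.

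**Other readings that the text allows** (losses at 50% and 80% full-scale power)
- Tertiles scored as a trend keep 79%: losses of 8.5 and 9.6 points.
- Quartiles scored as a trend keep 86%: losses of 5.6 and 6.1 points.
- Unordered tertiles (2 df) lose 17.4 and 19.9 points; unordered quartiles (3 df) lose 20.0 and 22.7.
- A uniform modifier cut at its median keeps 75%: losses of 10.4 and 12.1 points.
- Age truncated at 55, with an assumed underlying mean of 65 and SD of 8, keeps 66% at the median.
- A 90/10 split of a normal modifier keeps 34.2%: losses of 29.2 and 42.6 points.

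Each grouping examined loses power under a linear gradient. The amount ranges widely.

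**The case against.** A reader might infer that the plan splits all three variables in two, and so keeps at most 64% of the information and gives up 15 to 30 points of power. The documents do not support that. No grouping of BMI or age is stated, and the 0.75 mm cut is a stratification rule. Nor is 64% a ceiling, as the trend-scored and uniform cases show. The 15 to 30 points also presuppose 50% to 80% full-scale power; interaction tests are often weaker than that, and at 30% power the loss is 9 to 13 points. This objection stands, and it makes the figures conditional.

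Section 9.6.7.1 already leaves room for a full-scale interaction with body mass. That stands in part: no scale is stated there, age and baseline CIMT are not named, and it does not replace the test that 9.6.7.2 declares.

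A linear interaction can do worse than grouping when the pattern is a threshold or is not monotone, and nothing in the documents indicates the shape. This stands as a genuine downside.

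Finally, baseline CIMT is itself one of the outcomes in the 9.6.5.1 model, so as a modifier it would sit on both sides. Under randomization this affects the arms equally, and the stratum version has the same feature in coarser form. It is not a reason to prefer grouping.

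**Conclusion.** The point holds in a conditional form. Section 9.6.7.2 specifies a subgroup test for three continuous modifiers and leaves the groups undefined; a continuous interaction is the better test under a roughly linear gradient.

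The loss is about 15 to 30 points of power for two-group splits from 50/50 to 80/20, given a normal modifier, a linear gradient, two-sided 0.05 and an assumed 50% to 80% full-scale power. It is about 9 to 13 points at 30% power, and about 6 to 10 points for trend-scored tertiles or quartiles at 50% to 80%. None of these is a property of the plan itself, which states neither the groups nor the power.

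It would also be wrong to infer any effect on the main conclusions. The analysis is listed as ancillary, and the primary comparison does not depend on it. This is a worthwhile clarification of low severity.

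**What to change.** In section 9.6.7.2, state that the significance test for baseline CIMT, BMI and age uses the modifier as a continuous, centred variable interacting with the treatment effect of each efficacy model:
- CIMT and stiffness: treatment × time × modifier, with all lower-order terms.
- Cognition: treatment × modifier.

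Keep the subgroup effect sizes for description and as a check on linearity. Gender and smoking stay categorical.

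The cost is a short addition to the SAP, with no new data. The downside to acknowledge is that the test assumes an approximately linear gradient and may be weaker for a threshold or non-monotone pattern.
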